## 12.0 Descriptive Factors

- 12.1 Parameters followed for hematologic response (pick one): serum monoclonal protein  $\geq 1$  g/dL and urine monoclonal protein  $\geq 200$  mg/24 hours vs. serum monoclonal protein  $\geq 1$  g/dL only vs. urine monoclonal protein  $\geq 200$  mg/24 hours only vs. serum immunoglobulin free light chain  $\geq 10$  mg/dL with an abnormal free light chain ratio vs. bone marrow plasma cells  $>30\%$ . Distinguish between SPEP measurements versus quantitative IgA measurements for serum monoclonal protein.
- 12.2 MM risk categories (As per Appendix VII): High vs. standard/intermediate
- 12.3 MM patient frailty patient status (per Appendix I): fit vs. intermediate fitness vs. frail
- 12.4 Phase I only: Dose Level (to be assigned by Registration Office):  
-1 vs. 1 vs. 2 vs. 3 vs. 4

## 13.0 Treatment/Follow-up Decision at Evaluation of Patient

- 13.1 Patients who are responding

Patients who are sCR, CR, VGPR, PR, MR, or SD (or usCR, uCR, uVGPR, uPR, uMR) will continue treatment per protocol. Treatment may continue until disease progression as long as the patient continues to respond and does not have any unacceptable toxicity.

- 13.3 Criteria for Initiation of Event Monitoring

Patients who go off protocol treatment for the following reasons will go to the event monitoring phase per Section 4.2:

- Progressive multiple myeloma while on combination treatment with ibrutinib, lenalidomide and dexamethasone
- Patient requests to discontinue study treatment
- Patient develops an intercurrent illness that precludes further participation, or requires a prohibited concomitant treatment
- The Investigator withdraws the patient in the patient's best interests
- Patient is lost to follow-up (defined as the inability to contact the patient for more than 2 years)
- Administrative reasons (e.g., the patient is transferred to hospice care)
- An adverse event, which in the opinion of the Investigator, precludes further trial participation
- A dose omission of more than 28 days beyond the scheduled date of retreatment for ibrutinib or lenalidomide

All attempts should be made to complete the End of Study procedures if a patient goes off treatment early.

#### 13.4 Criteria for Study Discontinuation

The study may be temporarily or permanently discontinued at any site and at any time. Reasons for study discontinuation may include, but are not limited to, the following:

- Safety concerns
- Poor enrollment
- Non-compliance with the protocol, Good Clinical Practice guidances or other regulatory requirements by the Investigator(s)
- Request to discontinue the trial by a regulatory or health authority or an IRB
- Manufacturing difficulties/concerns

All Investigators and the requisite regulatory authorities will be notified if the study is suspended or terminated for safety reasons. In the case of such termination, the Investigator will notify the IRB.

#### 13.5 Failure to complete Cycle 1

Phase I Only: If a patient fails to complete the first cycle (each cycle=28 days) of the treatment for reasons other than toxicity, the patient will be regarded as inevaluable and will be replaced.

#### 13.6 Ineligibles

A patient is deemed *ineligible* if after registration, it is determined that at the time of registration, the patient did not satisfy each and every eligibility criteria for study entry. The patient may continue treatment off-protocol at the discretion of the physician as long as there are no safety concerns, and the patient was properly registered. The patient will go directly to the event-monitoring phase of the study (or off study, if applicable).

- If the patient received treatment, all data up until the point of confirmation of ineligibility must be submitted. Event monitoring will be required per Section 18.0 of the protocol.
- If the patient never received treatment, on-study material and the End of Active Treatment/Cancel Notification Form must be submitted. No further data submission is necessary.

#### 13.7 Major violation

A patient is deemed a *major violation*, if protocol requirements regarding treatment in cycle 1 of the initial therapy are severely violated that evaluability for primary end point is questionable. All data up until the point of confirmation of a major violation must be submitted. The patient will go directly to the event-monitoring phase of the study. The patient may continue treatment off-protocol at the discretion of the physician as long as there are no safety concerns, and the patient was properly registered. Event monitoring will be required per Section 4.2 of the protocol.

#### 13.8 Cancel

A patient is deemed a *cancel* if he/she is removed from the study for any reason before any study treatment is given. On-study material and the End of Active Treatment/Cancel Notification Form must be submitted. No further data submission is necessary.

## 14.0 Body Fluid Biospecimens

### 14.1 Summary Table of Research Blood and Body Fluid Specimens to be collected for this Protocol

Correlative Study (Section for more information)	Mandatory or Optional	Blood or Body Fluid being Collected	Type of Collection Tube (color of tube top)	Volume to collect per tube (# of tubes to be collected)	Baseline	Every cycle	End of treatment	Process at site?	Temperature Conditions for Storage /Shipping
BTK Signalosome	Mandatory	Bone marrow aspirate	Green Top tube	5 mL (2)	Baseline/ after registration but prior to treatment	Prior to addition of len to ibr- dex* and as clinically indicated***	Confirmed disease progression	No	On dry ice
Effect of Ibr on microenvironment	Mandatory	Bone marrow aspirate	Green Top tube	5 mL (1)	Baseline/ after registration but prior to treatment	Prior to addition of len to ibr- dex* and as clinically indicated***	Confirmed disease progression	No	At room temperature
Effect of Ibr on microenvironment	Mandatory	Peripheral Blood	Green Top tube	5 mL (2)	Baseline/ after registration but prior to treatment	Every 3 cycles while patient continues on treatment**		No	At room temperature
Effect of Ibr on platelet aggregation (Platelet surface glycoprotein by flow cytometry, blood)	Mandatory	Peripheral Blood	Yellow Top tube	5 ml	Baseline/ after registration but prior to treatment	Every cycle for first 3 cycles; then every 3 cycles while patient continues on treatment for up to 12 cycles	Confirmed disease progression	Yes	At room temperature

Correlative Study (Section for more information)	Mandatory or Optional	Blood or Body Fluid being Collected	Type of Collection Tube (color of tube top)	Volume to collect per tube (# of tubes to be collected)	Baseline	Every cycle	End of treatment	Process at site?	Temperature Conditions for Storage /Shipping
Effect of Ibr on platelet aggregation Platelet aggregation study (functional)	Mandatory	Peripheral Blood	Special tubes to be supplied by heme lab	9 ml (4)	Baseline/ after registration but prior to treatment	Every 3 cycles while patient continues on treatment for up to 12 cycles	Confirmed disease progression	Yes	At room temperature

\*Phase II only

\*\*Additional samples to be drawn in-between every 3 cycles in case there is confirmed disease progression

\*\*\* Additional samples to be drawn if a bone marrow is done for confirmation of response or as otherwise clinically indicated.

ibr=ibrutinib, len=lenalidomide, dex=dexamethasone

## 14.2 Collection and Processing

No specific instructions other than outlined in table 14.1

## 14.3 Shipping and Handling

14.31 **Kits will not be used for this study.**

## 14.33 Handling Specimens

Samples should be transported same day (if from Mayo Clinic, Florida) or shipped by overnight mail (if from Mayo Clinic in Arizona or Minnesota) on dry ice and dispatched only on Monday-Thursday for a receipt in Jacksonville on Tuesday-Friday.

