## 1.7 Correlative Research

1.71 *To determine the role of members of the BTK signalosome in achievement or lack thereof of response to ibrutinib:* The variability in extent of response to a therapeutic agent may suggest underlying adaptability of the MM clone through components of the BTK signalosome. Patients with B-cell malignancies treated with ibr demonstrate upregulation of p-Akt and p-Erk (downstream mediators of BTK) in some (but not all) cases, suggesting that these pathways may contribute to survival of the malignant clone. It was also concluded in this work that these cells might not be dependent upon the proximal BTK pathways mediated apoptosis and thus, resistant to killing by ibr. To address this question we will establish the profile of BTK signalosome for each patient through determination of the mRNA (RT-PCR/nanostring assay; whole exome sequencing (WES), transcriptom analysis) and protein expression (western blot analysis) of members of the BTK signaling pathway and look for associations between this and eventual response (or lack thereof) to the treatment. The said tests will be done analyzing the CD138+ cells enriched from the bone marrow samples collected at baseline, after 1 month of treatment with ibr alone and then at the time of disease progression. This will help explore mechanisms of acquired resistance to ibr. In MM. We will also look for pAKT, pS6 and pERK as indirect pharmacodynamic biomarkers analyzed in patient's PBMC collected as a peripheral blood sample at baseline and then after 1 cycle of treatment with ibr, prior to adding the len/ dex.

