1.72 *To explore biologic effects of ibrutinib on microenvironment in MM and correlate with response to treatment:* In cancer redirection of host immunity from a predominant Th2 to Th1 response can deliver antitumor response. Ibr can bind to ITK, a member of the TEC-kinase family, which mediates TCR signaling through PLC $\gamma$ , NFAT, NF- $\kappa$ B and MAPK. This results in activation and proliferation of CD8+ cells. Our hypothesis is that ibr alters the Th2:Th1 balance in the blood and bone marrow microenvironment, skewing towards a more Th1 profile and this may translate into its clinical efficacy. We further hypothesize that the robustness of the Th1 response will direct ibr's depth of response. We will assess this in bone marrow samples comparing the baseline sample to one collected after 1 cycle of treatment with ibr using the MultiOmyx Tumor Infiltrating Lymphocytes panel for T helper (CD4+), Treg (FOXP3+), T cytotoxic (CD8+), B cells (CD20+), macrophage (CD68+), NK cells (CD56+), immunosuppression (PD-L1), CD138+, CD38+, ITK and BTK. Furthermore, BTK/ITK occupancy by ibr has been associated with response rates in other B-cell malignancies where this is an effective agent (CLL) but this has never been tested in MM. This assay will be performed to assess target coverage in bone marrow samples obtained from patients at the end of 1 cycle of treatment with ibr. In addition, PBMC samples (2 ml of whole blood with heparin) from baseline and after 1 cycle of treatment with ibr will be assessed for:

- Th1 cells (live+, CD19-, CD3+, CD4+, CD8-, IFNg+)
- Th2 cells (live+, CD19-, CD3+, CD4+, CD8-, IL4+)
- Th17 cells (live+, CD19-, CD3+, CD4+, CD8-, IL17+)
- Treg cells (live+, CD19-, CD14-, CD3+, CD4+, CD25+, CD127-, FOXP3, CCR4+)

1.73 *To explore compliance to treatment:* The proposed regimen in this clinical trial is all-oral. Data from other malignant and non-malignant diagnoses (e.g., CML,

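### Section 14.33 ships research samples overnight on dry ice, while Table 14.1 puts the unprocessed immune-cell blood and marrow at room temperature

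*Combined protocol and SAP*

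**What the plan says.** Two places in section 14 tell staff at what temperature to ship research samples.

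- **Section 14.33 (Handling Specimens)** states one rule for samples in general. For Florida it reads "Samples should be transported same day (if from Mayo Clinic, Florida". For the other two campuses, tubes are to be "shipped by overnight mail (if from Mayo Clinic in Arizona or Minnesota) on dry ice and dispatched only on Monday-Thursday", for receipt in Jacksonville on Tuesday to Friday. No sample type is named or excepted.
- **Table 14.1** has a column headed "Temperature Conditions for Storage /Shipping", so it also governs shipping. One of its five rows, the BTK signalosome marrow, is on dry ice. The other four are marked "At room temperature": microenvironment marrow, microenvironment blood, platelet surface glycoprotein, and functional platelet aggregation. A separate column shows whether the sample is processed at the collecting site.

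Section 14.2 adds nothing to settle the matter: "No specific instructions other than outlined in table 14.1". Section 14.31 says that no kits will be used, so no kit instructions stand between the protocol and the person packing the box.

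Three sections describe the use of the microenvironment samples. Section 1.72 lists T-cell panels on mononuclear cells from heparinised blood, beginning with "Th1 cells (live+, CD19-, CD3+, CD4+, CD8-, IFNg". Section 14.42 plans flow cytometry for Th1 and Th2 cells in both blood and marrow. Section 16.442 plans percentages of immune-cell populations in both, their changes over time, and Wilcoxon rank sum tests against response.

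**The concern.** A coordinator in Arizona or Minnesota cannot obey both instructions for the microenvironment tubes: 14.33 puts them on dry ice and Table 14.1 keeps them at room temperature. If 14.33 is followed, unprocessed blood and marrow meant for flow cytometry would arrive frozen.

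The loss would not be easy to repair. The baseline tubes are drawn after registration and before treatment, so they cannot be taken again once treatment has started. Section 16.442 looks at change across time, so a spoiled baseline removes that patient from every change-from-baseline summary of the measure. If some sites follow 14.33 and others the table, handling would differ by site, and part of any difference in cell percentages could reflect transport rather than treatment. The collections are mandatory, and the marrow comes from an invasive procedure.

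**Working it through.** The plan gives no figure to reproduce here, and no sample-size or power formula applies. The check sets each row of Table 14.1 against the 14.33 rule for Arizona and Minnesota, which is overnight on dry ice.

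| Row of Table 14.1 | Processed at site | Temperature in Table 14.1 | Against 14.33 |
|---|---|---|---|
| BTK signalosome, marrow | No | Dry ice | Agrees |
| Microenvironment, marrow | No | Room temperature | Direct conflict |
| Microenvironment, blood | No | Room temperature | Direct conflict |
| Platelet surface glycoprotein, blood | Yes | Room temperature | Temperature differs; 14.33 not clearly applicable |
| Platelet aggregation (functional), blood | Yes | Room temperature | Temperature differs; 14.33 not clearly applicable |

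**Row count.** 1 agrees + 2 conflict directly + 2 differ in stated temperature but are processed at site = 5. So 4 of 5 rows differ from 14.33 in stated temperature, and 2 of 5 conflict in a way that reaches a shipped, unprocessed tube.

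**Sites.** 14.33 names three campuses. On the natural reading, the dry-ice instruction applies to the two that use overnight mail.

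**From conflict to consequence.**

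1. The two microenvironment rows are not processed at site, so the tubes travel as drawn.
2. Sections 14.42 and 16.442 analyse both by flow cytometry, and the blood panels in 1.72 gate on live cells.
3. Freezing unprocessed whole blood or marrow would be expected to destroy the cells that such a gate selects. The documents do not say this. It is a technical inference, and the room-temperature entry in the table is consistent with it.
4. The objective affected is 2.42, on the microenvironment and its correlation with response. Its analysis is under 16.44, the exploratory correlative outcomes.

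**Patients.** The planned maximum is 63 overall: 24 in phase I, 34 in phase II and 5 extra (24 + 34 + 5 = 63). The plan does not divide this by site, so the number whose samples would leave Arizona or Minnesota cannot be derived.

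**The case against.** The best reply is that the plan already holds the answer. The table entry is specific, the sentence in 14.33 is general, and 14.2 points the reader to the table. A site that reads the row would ship at room temperature and lose nothing. This stands in part: the harm is conditional on staff following 14.33. But 14.33 is the section on handling, it carries no exception, and nothing says which instruction prevails.

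Three limits also stand. The text between 14.31 and 14.33 is not in the available copy and may give destinations or handling by sample. The dry-ice phrase could be read to cover the Florida transport as well, which would widen the conflict to all three campuses. And the live-cell gate is stated only for blood; 1.72 sends the marrow to a multiplexed tissue panel, so the case for marrow rests on the flow cytometry in 14.42 and 16.442.

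A reader might also infer more than the documents support:

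- **That the platelet tests are ruined.** Both platelet rows, including "Platelet surface glycoprotein by flow cytometry, blood", are marked as processed at site, and the aggregation tubes come from the haematology laboratory. Nothing shows fresh platelet tubes being mailed on dry ice, so harm to objective 2.44 is not established.
- **That the BTK marrow row is wrong too.** Section 1.71 describes "analyzing the CD138+ cells enriched from the bone marrow samples", and one may ask how that is done on frozen, unprocessed marrow. But 14.33 and Table 14.1 agree on dry ice for this row, and 14.41 lists mRNA and western-blot readouts. Whether unfrozen transit would serve better is a laboratory trade-off, not a contradiction in the plan.
- **That a stated share of patients is lost.** Any such figure needs accrual by site, which is not given.
- **That Friday draws are unprotected.** Dispatch on Monday to Thursday already signals when to draw, and visits have a window of 3 days either way.

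**Conclusion.** The inconsistency is real and narrow. Four of the five rows in Table 14.1 differ from 14.33 in stated temperature. For two of them, the microenvironment marrow and the microenvironment blood, the conflict is direct because unprocessed tubes are shipped. Following 14.33 as printed would be expected to compromise the flow-cytometry results for objective 2.42 from Arizona and Minnesota.

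This rests on two assumptions: that freezing unprocessed tubes spoils live-cell gating, and that the text missing between 14.31 and 14.33 holds no exception by sample type. The effect is confined to exploratory correlative results. The primary response rate, the interim and final decision rules, the safety stopping rules and the sample size are untouched. It merits correction because the samples are mandatory, the baseline cannot be redrawn after treatment starts, and the remedy is nearly free.

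**What to change.** Reword 14.33 so that each sample is shipped at the temperature given for its row in Table 14.1, with dry ice only for the BTK signalosome marrow. The overnight-mail and Monday-to-Thursday dispatch rules can stay as they are. While the section is open, a short statement of where the platelet samples are tested would remove the remaining doubt about whether 14.33 applies to them.

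The cost is one sentence in the next amendment and a note to the sites. No visit, tube, volume, assay or analysis changes. If microenvironment samples have already been sent, check from the shipping records how they travelled before running the analysis in 16.442.

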## 14.4 Background and Methodology

14.41 BTK signalosome: The variability in the extent of clinical response may suggest underlying adaptability of the MM clone mediated through components of the BTK signalosome. Patients with B-cell malignancies treated with ibrutinib demonstrate upregulation of p-Akt and p-Erk (downstream mediators of BTK) in some (but not all) patients and suggest that these downstream pathways may contribute to the survival of the malignant clone. They also concluded that these cells might not be dependent upon the proximal BTK pathways mediated apoptosis and thus resistant to killing by ibrutinib. To address this question we will establish the profile of BTK signalosome for each patient through determination of the mRNA (RT-PCR/ nanostring assay) and protein expression (western blot analysis) of members of the BTK signaling pathway. Samples: Bone marrow samples (2 x 5ml green top tubes) will be collected at prior to initiating the ibrutinib therapy, at the time of disease progression while on ibr therapy or if there is a lack of response noted to single-agent ibr at the time points specified in the study schema. In the form of expected results, we anticipate (a) variability in the expression and phosphorylation status of various members of BTK pathway (Syk, Lyn CD79 FYN) and their targets (ERK, AKT, NFKB and Bcl-2, Mcl-1, XIAP, MYC, CD40 and CFLAR) (b) and predict correlation of this variability with the depth of response achieved in that patient. Furthermore, this will also help identify the signalosome pattern that may suggest lack of response/progression to single-agent ibr in MM patients.

14.42 Effect of ibrutinib on MM microenvironment: In cancer redirection of host immunity from a predominant Th2 to Th1 response can deliver antitumor response. Ibr can bind to ITK, a member of the TEC-kinase family mediates TCR signaling through PLC $\gamma$ , NFAT, NF- $\kappa$ B and MAPK. This results in activation and proliferation of CD8+ cells. Our hypothesis is that ibr alters the

Th2:Th1 balance in the blood and bone marrow microenvironment skewing towards a more Th1 profile and this may translate into its clinical efficacy. We further hypothesize that the robustness of the Th1 response will direct ibrutinib's depth of response. Blood and bone marrow will be evaluated/quantified for Th1 and Th2 cells (by flow cytometry). Changes in the cellular profile as well as respective cytokine (such as IL2, IL12, INF $\gamma$  and IL4, IL5, IL13 and IL10, respectively) will be measured (for cytokine we will use the multiplex assay). Blood (2 x 5ml green top tubes) and bone marrow samples (1 x 5ml green top tubes) will be collected at any time prior to initiating the ibrutinib therapy. Serial bone marrow samples will be collected at the time of disease progression while on ibr therapy or if there is a lack of response noted to single-agent ibr at the time points specified in the study schema. Furthermore, serial blood samples will be collected every 3 months while the patient remains on study treatment and additionally at the time of disease progression while on ibr therapy or if there is a lack of response noted to single-agent ibr at the time points specified in the study schema.

We anticipate that ibr treatment (a) will result in increase in Th1 cells both in the blood and the bone marrow with bone marrow demonstrating a higher percentage of Th1 cell activity and that (b) extent of immune cellular response will correlate with the robustness of the clinical response and that (c) the cytokine profile will mimic this cellular pattern and can be used to predict immune cellular response to ibrutinib. Identification / validation of immune restoration ability of ibr and its correlation with disease response will be a highly novel observation and will define a unique role and mechanism of ibrutinib in MM.

14.43 Effect of ibrutinib on platelet aggregation: While it is known that ibrutinib causes platelet dysfunction, the mechanistic pathway is not clearly understood. *In-vitro* studies have shown possible interaction with collagen receptor GPVI and also affect platelet adhesion on von Willebrand factor. To further characterize the bleeding events in ibrutinib-treated patients, we will investigate the effect of ibrutinib on platelet aggregation *ex vivo*. Platelet flow cytometric analysis is the preferred method to assess quantitative surface glycoprotein (GP) deficiencies. GP expression levels can be measured by using fluorescent-conjugated GP-specific antibodies and their fluorescent intensities can be compared to normal ranges of various glycoproteins. Platelet aggregometry uses a combination of laser light scattering to monitor the continuous formation of platelet microaggregates. The test is sensitive enough to detect aggregates containing only two or three platelets. The method uses of a panel of platelet agonists (eg, collagen, ADP, epinephrine, ristocetin) at a range of concentrations that triggers classical platelet responses, including shape change as well as primary and secondary aggregation. The recorded response depends upon the normal functioning of the platelet, the presence of inhibitors of platelet function, as well as the concentration of agonist, facilitating detection of classical platelet disorders based upon the pattern of aggregation.

